### 16.2 The entering of data into the eCRF

All entries, corrections, and alterations in the eCRF are to be made by the Investigator or designated site personnel. Neither the Monitor nor any other study team member besides site personnel may enter data in the eCRF. All data should be entered in English. The eCRFs should be completed as soon as possible during or after the subject's visit. If some assessments are not done, or if certain information is not available, not applicable, or unknown, the Investigator or assigned clinical staff should record such information in the eCRF.

The Investigator must verify that all data entries in the eCRFs are accurate and correct and will be required to electronically sign off the clinical data. This will be performed by means of

the Investigator's unique User ID and password; date and time stamps will be added automatically at the time of electronic signature.

### **16.3 The query process**

The Monitor will review the eCRFs and evaluate them for completeness and consistency. Data in the eCRF will be compared with the respective source documents to ensure that there are no discrepancies for critical data as described in the RBM plan.

If corrections are needed, queries will be raised within the eCRF, either as a result of built-in edit checks or manually raised by the Monitor. An appropriate member of the site staff will answer the queries in the eCRF either by correcting the data or by entering a response to the query. The Monitor will either approve the answer/correction or re-issue the query.

### **16.4 Audit trail**

All entries in the eCRF will be fully recorded in a protected audit trail. Once clinical data have been saved, corrections to the data fields will be audit trailed, meaning that the reason for change, the name of the person who made the change, together with time and date will be logged.

### **16.5 External data**

External data consists of data that is not recorded in the eCRF. Data may be received in electronic format. Key variables are defined to uniquely identify each sample record. File and data formats are agreed with the external data provider.

### **16.6 Medical coding**

Medical coding will be performed by trained personnel at CTC. AEs and medical/surgical history verbatim terms will be coded using the Medical Dictionary of Regulatory Activities (MedDRA; latest version available at start of eCRF development). Prior and concomitant medications will be coded according to the WHO Anatomic Therapeutic Chemical (ATC) classification system. All coding will be approved by the Sponsor prior to database lock.

### **16.7 Database lock**

When all data has been entered and discrepancies solved, clean file will be declared, the database will be locked, and the data will be analyzed.

## 17 STATISTICAL METHODS AND DETERMINATION OF SAMPLE SIZE

The principal features of the statistical analysis to be performed are described in this section. A more technical and detailed elaboration of the principal features will be presented in a separate Statistical Analysis Plan (SAP), which will be signed and approved prior to database lock.

### 17.1 General

Continuous data will be presented in terms of evaluable and missing observations, arithmetic mean, standard deviation (SD), median, minimum and maximum value, Q1-Q3 (interquartile range [IQR]).

Categorical data will be presented as counts and percentages. When applicable, summary data will be presented by each group (ZYN Dry or ZYN Moist), and by assessment time. Individual subject data will be listed by subject number, treatment arm (ZYN Dry or ZYN Moist), and, where applicable, by assessment time.

All descriptive summaries and statistical analyses will be performed using SAS Version 9.4 or later (SAS Institute, Inc., Cary, NC).

Baseline will be defined as the last data collected before subjects are randomized into substitution of tobacco-based snus with either ZYN Dry or ZYN Moist.

No adjustment for multiple comparisons will be made.

No imputation of missing data will be performed.

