On the third treatment visit (Visit 4, Day 14), a routine dental examination (including assessment of the amount of plaque and oral mucosal lesions), sampling of specimen for counting the number of mutans streptococci and lactobacilli as well as collection of saliva for assessment of BoE. Data regarding dental plaque acidogenicity will be collected before and after a 1 min mouth rinse with 10 mL of a 10% sucrose solution and assessed at 0, 2, 5, 10, 15, 30, 45, and 60 min.

On the fourth treatment visit (Visit 5, Day 28), a routine dental examination (including assessment of the amount of plaque, oral mucosal lesions, and tooth discoloration), sampling of specimen for counting the number of mutans streptococci and lactobacilli as well as collection of saliva and urine for assessment of BoE will be performed. Data regarding plaque acidogenicity will be collected before and after a 1 min mouth rinse with 10 mL of a 10% sucrose solution and assessed at 0, 2, 5, 10, 15, 30, 45, and 60 min. A biopsy of the oral mucosa will also be collected.

AEs will be collected by subject interview from the start of substitution of tobacco-based snus with ZYN (Visit 3) until the last treatment visit (Visit 5).

The total duration for each subject in the study will be 8 weeks, not including the preceding screening period.

See [Table 8.1-1](#) for schedule of events applicable for each treatment visit.

Study assessments are described in Section [11](#).

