### 17.2 Determination of sample size

The primary endpoint is the difference between ZYN Dry and ZYN Moist in terms of changes in dental plaque acidogenicity, assessed by measuring pH in plaques, after substitution of tobacco-based snus for 4 weeks. No formal sample size calculation has been performed as available data for the two study product types are lacking. Based on previous experiences using this method, 20 subjects are considered to generate sufficient data for the purpose of this study. Hence, with an estimated dropout rate of 15% a total of 46 subjects will be randomized to achieve 40 fully evaluable subjects.

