## 17.5 Analysis of the primary endpoint

### 17.5.1 *Difference in dental plaque acidogenicity between ZYN Dry and ZYN Moist*

The primary endpoint is the difference between ZYN Dry and ZYN Moist in terms of changes in dental plaque acidogenicity, assessed by measuring pH in plaques, after substitution of tobacco-based snus for 4 weeks. Assessment of dental plaque acidogenicity will be described using AUC6.2 to the observed dental plaque acidogenicity and presented using summary statistics as described in Section [17.1](#).

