## 17.6 Analysis of secondary endpoints

### 17.6.1 *Dental plaque acidogenicity*

The difference in dental plaque acidogenicity will be calculated from the start of tobacco-based snus substitution with either ZYN Dry or ZYN Moist (Visit 3) until the end of the study (Visit 5). The assessment of dental plaque acidogenicity will be described using AUC6.2 to the observed dental plaque acidogenicity and presented using summary statistics

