### 17.6.2 *Number of cariogenic microorganisms in dental plaque*

The difference in the number of cariogenic microorganisms in dental plaque will be evaluated, graded, and calculated from the start of tobacco-based snus substitution with either ZYN Dry or ZYN Moist (Visit 3) until the end of the study (Visit 5) and presented through descriptive statistics.

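### The stated change analyses rest on Day 28 completers and leave out Day 14, so the Dry–Moist difference may be biased if response-related dropout differs between arms

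*Protocol*

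**What the plan says.** Section 17.5.1 defines the primary endpoint through "changes in dental plaque acidogenicity, assessed by measuring pH in plaques, after substitution of tobacco-based snus for 4 weeks". The AUC6.2 results are to be "presented using summary statistics as described in Section" 17.1. Baseline (17.1) is the last value before randomization, which is Visit 3.

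For the secondary plaque pH endpoint, 17.6.1 takes the difference from the start of substitution "with either ZYN Dry or ZYN Moist (Visit 3) until the end of the study (Visit 5"). Sections 17.6.2 (microorganisms) and 17.6.3 (plaque score) use the same interval, "Visit 3) until the end of the study (Visit 5) and presented through descriptive statistics". Section 17.7.1 does the same for saliva biomarkers.

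The trial also assesses subjects between those visits: "On the third treatment visit (Visit 4, Day 14), a routine dental examination" takes place (Section 8.1), with the plaque score, cultures, a saliva sample and the full 0 to 60 minute sucrose challenge. Table 8.1-1 confirms this.

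On missing data, 17.1 says: "No imputation of missing data will be performed". Section 17.2 randomizes 46 subjects to obtain 40 evaluable, "with an estimated dropout rate of 15"%. Section 17.3.1 puts all randomized subjects in the full analysis set. Section 17.1 also allows summaries by arm and assessment time where applicable.

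**The concern.** Read together, these sections give a subject who leaves between Day 14 and Day 28 no value for any stated change, even with a complete post-switch pH curve, culture and plaque score. The analysis set is labelled all randomized, but the comparison is of those who stayed.

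Dropout could differ by arm. The study is open-label, the products differ in nicotine content (6 and 9 mg, Table 10.1-1) and in pouch size, moisture and salt (6.1), and subjects must give up all other nicotine (9.6.1). Under 9.8.3, subjects withdrawn for an adverse event at least possibly related to the product are not replaced, whereas others may be. If those who leave one arm are those whose plaque worsened early, that arm's Day 28 change looks better than it is. The Day 14 values that could correct this are in the database but play no part in the stated comparison.

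**Working it through.** **Numbers at risk.** The plan's 46 reproduces as 40 × 1.15 = 46. (Dividing instead gives 40/0.85 = 47.1, or 48 in two equal arms; the gap does not matter here.) The plan implies 46 − 40 = 6 non-evaluable subjects (13%), or 46 × 0.15 = 6.9 at the stated rate. Only those lost after Day 14 concern this point; the protocol does not say how many that is.

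**How the bias arises.** Suppose Day 14 and Day 28 changes are bivariate normal with SD 1 and correlation ρ, and dropout after Day 14 depends on the Day 14 change. Then:

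- bias of an arm's completer mean = ρ × (shift of the Day 14 mean among those who stay);
- bias of the difference = ρ × (shift in one arm − shift in the other).

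Equal shifts cancel. Using Day 14, the arm mean is estimated as the completer Day 28 mean + slope × (Day 14 mean of all − Day 14 mean of completers), which removes the shift if missingness depends only on observed values.

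**Large-sample simulation.** There were 400,000 subjects per arm. All inputs are assumptions: log-odds of dropout 1 per SD of Day 14 change, no true difference. The table gives the bias of the completer-only difference, in SDs of change.

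| Dropout pattern | ρ = 0.3 | ρ = 0.5 | ρ = 0.7 |
|---|---|---|---|
| Same process, 15% in both arms | −0.004 | 0.002 | 0.000 |
| 15% in both, response-related in one arm only | −0.041 | −0.062 | −0.095 |
| Response-related in both, 25% vs 5% | −0.051 | −0.084 | −0.117 |
| Opposite relations, 15% in both | −0.078 | −0.130 | −0.186 |

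With Day 14 used, every entry is within 0.004 of zero. The formula checks: with 15% response-related dropout the biases in the first arm are −0.040, −0.065 and −0.093, and dividing each by its ρ gives a shift of −0.13 each time.

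**Simulation at the planned size.** There were 23 per arm, correlations between visits of 0.5, 0.7 and 0.8, and no true difference. After Day 14, 6 of 23 leave one arm because of the worst early change and 1 of 23 leaves the other (7/46 = 15%). Units are SDs of a single-visit value.

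- The plan's own analysis, unadjusted Day 0 to Day 28 change in completers: bias 0.13 to 0.21 SD in size.
- Baseline-adjusted completers: bias −0.112, −0.119, −0.105 (SE 0.285, 0.235, 0.195), that is 0.39, 0.51 and 0.54 of one SE.
- Adding Day 14 by maximum likelihood: bias −0.002, 0.002, 0.002 (SE 0.291, 0.239, 0.197). The SE is 1 to 2% larger.

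**If dropout is random.** There is no bias to remove. Adding Day 14 to a baseline-adjusted analysis cuts variance by only 1 to 3% (ratios 0.967 to 0.990). Against the plan's unadjusted change the cut is about 10 to 25%, so most of that gain comes from baseline adjustment.

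**What Day 14 cannot show.** Table 8.1-1 schedules polishing at Visits 2 and 3 only. Visits 3 and 5 each fall 28 days after polishing; Visit 4 falls 14 days after.

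**The case against.** The strongest reply is that this belongs to the statistical analysis plan. Section 17 claims to give only principal features, and the model and the use of intermediate visits are often settled later. That is fair for the covariance structure or the software. But the Visit 3 to Visit 5 interval and the no-imputation rule are written into the protocol: they are choices, not silence. The analysis plan could add a model, yet nothing here calls for one.

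Several further objections stand and limit the point:

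- A reader might infer that dropout related to early response biases the comparison in itself. It does not: with the same process in both arms the difference is unbiased. Nor does the protocol show that dropout will differ; none of the withdrawal reasons in 9.8.1 is a plaque measurement.
- A reader might infer that the Day 14 data go unused. Section 17.1 allows for them in summaries and listings by assessment time.
- A reader might blame the no-imputation rule. A likelihood-based model imputes nothing; the cause is the completer-only change.
- A reader might expect Day 14 to show whether the effect had settled by week 4. The polishing schedule confounds that within an arm, though not the contrast between arms at Day 14.

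The 6 versus 1 pattern is also extreme and assumed, and a normal model will not suit every secondary endpoint.

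**Conclusion.** The point holds in limited form. The stated comparison is one of Day 28 completers under an all-randomized label, and the Dry–Moist difference may be biased if response-related dropout differs between arms. The size is about 0.1 to 0.2 SD in the extreme case at the planned size, 0.04 to 0.19 SD over the milder and opposite patterns in the table, and about 0 when the arms share one process. These figures rest on assumed correlations and dropout mechanisms, since the protocol gives neither. The 4-week time point itself agrees with the objective and is not in question.

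**What to change.** In Section 17, for AUC6.2, and for log CFU and mean plaque score where a normal model is reasonable, add to the descriptive tables a likelihood-based repeated-measures model of Day 14 and Day 28. Include arm, visit, arm-by-visit, Day 0 baseline and baseline-by-visit, with unstructured covariance (three parameters for two visits). Include every randomized subject with any post-switch value. Report the Day 28 arm contrast with its confidence interval as the main result. State that the Day 0 to Day 14 change within an arm will not be used to judge whether the effect has settled.

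The no-imputation sentence can stay. The cost is some wording in Section 17 and the analysis plan, a little more programming, and a missing-at-random assumption. Subjects lost before Day 14 still contribute nothing after baseline.

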### 17.2 Determination of sample size

The primary endpoint is the difference between ZYN Dry and ZYN Moist in terms of changes in dental plaque acidogenicity, assessed by measuring pH in plaques, after substitution of tobacco-based snus for 4 weeks. No formal sample size calculation has been performed as available data for the two study product types are lacking. Based on previous experiences using this method, 20 subjects are considered to generate sufficient data for the purpose of this study. Hence, with an estimated dropout rate of 15% a total of 46 subjects will be randomized to achieve 40 fully evaluable subjects.

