## 8 STUDY DESIGN

### 8.1 Overall study design and schedule of events

This is an open-label, two-armed, randomized, longitudinal study, designed to assess the effects on dental plaque acidogenicity and other oral variables in current, daily users of tobacco-based snus who completely substitute their snus use with either ZYN Dry or ZYN Moist nicotine pouches (NPs). The IPs are unflavored (Smooth) or flavored (Cool Mint and Citrus) NPs and of different nicotine strengths (ZYN Dry 6 mg and ZYN Moist 9 mg).

The study will include 46 randomized subjects with the aim to achieve 40 fully evaluable subjects. The subjects are healthy male or female tobacco-based snus users aged  $\geq 21$ - $\leq 55$  years who have used tobacco-based snus for  $\geq 1$  year, with a minimum weekly consumption of 3 or more cans. An effort will be made to randomize at least 5 female subjects per treatment arm in the study (each arm consisting of 23 subjects in total).

The subjects report to the clinic for a screening visit (Visit 1) followed by 4 treatment visits (Visit 2-5) on separate days. The screening (Visit 1) will take place within 5 weeks prior to Visit 2 and will include an eligibility check, including evaluations of tobacco/nicotine use, a brief oral examination, urine pregnancy testing (women of childbearing potential only), and collection of medical history. Also, the salivary secretion rate and buffer capacity will be assessed (see [Table 8.1-1](#) for details). At the end of the screening, the subjects will be asked about flavor preferences on IPs.

Before each treatment visits (Visit 2-5; Day -28, Day 0, Day 14, and Day 28, respectively), scheduled at the same time of the day for each subject, the subjects will refrain from approximal tooth cleaning for 48 h and toothbrushing for 24 h prior to the visits. Also, the subjects will be instructed not to eat, drink, chew gum, or any other mouth related procedures 1 h before the visits and during the visits.

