### 9.3 Number of subjects

Forty-six (46) subjects will be included in the study. Approximately 60 subjects will be screened with the aim of achieving 46 randomized subjects and 40 fully evaluable subjects. A fully evaluable subject is defined as a subject who has used the IPs for 4 weeks and who has completed all study visits. An effort will be made to randomize at least 5 female subjects to each treatment arm (each consisting of 23 subjects in total), however a minimum of 2 randomized female subjects in each treatment arm will be considered acceptable.

For replacements of subjects who discontinue from the study, see Section [9.8.3](#).

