### 9.8.3 *Subject replacement*

Subjects who are prematurely withdrawn from the study may be replaced at the Sponsor's discretion after consultation with the PI. Subjects prematurely withdrawn due to AE(s) assessed as at least possibly related to the IP will not be replaced.

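### The 15% dropout allowance is applied as 40 × 1.15, so 46 randomized gives about 39 fully evaluable subjects before any replacement, not 40 (minor correction)

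*Protocol*

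**What the plan says.** Section 17.2 explains that there was no formal sample size calculation, because data on the two product types were lacking. It then gives an experience-based number, "20 subjects are considered to generate sufficient data for the purpose of this study", and moves straight to the number to randomize: "Hence, with an estimated dropout rate of 15% a total of 46 subjects will be randomized to achieve 40 fully evaluable subjects". The statistical methods part of the synopsis says the same.

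Elsewhere 40 is described as an aim. Section 8.1 has "The study will include 46 randomized subjects with the aim to achieve 40 fully evaluable subjects", and section 9.3 and the synopsis are in the same vein. Section 9.3 gives arms of 23 and defines the term being counted: "A fully evaluable subject is defined as a subject who has used the IPs for 4 weeks and who has completed all study visits". It also refers to section 9.8.3 on replacement, which begins "Subjects who are prematurely withdrawn from the study may be replaced". Replacement is left to the sponsor's discretion after consulting the principal investigator, and it is ruled out for withdrawals due to adverse events judged at least possibly related to the product.

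**The concern.** Section 17.2 presents 46 as the consequence of two inputs, a target of 40 and a dropout rate of 15%. A dropout rate is normally read as a proportion of those randomized. On that reading 46 does not follow: the 15% has been added to the number of completers instead of being taken off the number randomized.

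This sentence is the only numerical basis the protocol gives for the size of the trial. A reader who relies on it will expect 40 evaluable subjects when the stated inputs give about 39. What is at stake is the accuracy of a stated figure. No power statement, error rate or decision rule rests on it.

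**Working it through.** **Inputs**
- Target of fully evaluable subjects: 40 (17.2; also the synopsis, 8.1 and 9.3).
- Dropout: 15%, given as an estimate (17.2 and synopsis).
- Number randomized: 46 (17.2, 8.1, 9.3), in two arms of 23 (9.3).

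**Step 1: reproduce the protocol's figure.** Multiplying the target by (1 + dropout) gives 40 × 1.15 = 46.0 exactly, or 20 × 1.15 = 23.0 per arm. This appears to be how 46 was obtained. The 6 extra subjects are 6/40 = 15% of the completers.

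**Step 2: apply the rate to those randomized.** The number needed is target/(1 − dropout) = 40/0.85 = 47.06. That rounds up to 48 for two equal arms (20/0.85 = 23.5, so 24 per arm). The stated figure is 2 lower.

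**Step 3: what 46 gives at 15%.** Expected evaluable = 46 × 0.85 = 39.1, which is 0.9 below the target.

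**Step 4: what dropout 46 can absorb.** Going from 46 to 40 is a loss of 6/46 = 13.0%. Check: 46 × (1 − 6/46) = 40.

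**Step 5: chance of reaching 40.** Assume independent dropout and no replacement, so that the number evaluable is binomial.

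| Enrolled | Dropout | Expected evaluable | P(at least 40) |
|---|---|---|---|
| 46 | 15% | 39.1 | 0.45 |
| 46 | 14% | 39.6 | 0.53 |
| 46 | 13% | 40.0 | 0.61 |
| 47 (one replacement) | 15% | 39.95 | 0.59 |
| 48 (two replacements, or 48 from the start) | 15% | 40.8 | 0.71 |

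The replacement rows treat each replacement as one more subject with the same 15% risk of dropping out. The probability crosses one half with a one-point change in the dropout rate, or with a single replacement.

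**The case against.** The case for leaving the text alone is that the discrepancy is trivial. It amounts to less than one expected subject, the 15% is itself an estimate, and 40 is called an aim. There is no alpha, power or effect size behind the number. The full analysis set in 17.3.1 is all randomized subjects, so being fully evaluable does not define an analysis population. The primary endpoint in 17.5.1 is presented with summary statistics, and 39 instead of 40 changes no planned inference. Section 9.8.3 also allows lost subjects to be replaced. All of this stands and keeps the point minor.

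It does not make the sentence correct. Section 17.2 attributes the step from 40 to 46 to dropout alone and does not mention replacement. Replacement is optional and is not available for every withdrawal, so it cannot be taken to have been built into the 46.

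Two stronger readings are tempting, and the document supports neither. A reader might infer that the trial will miss its target more often than not. The 0.45 in the working is below one half only at 15% dropout with no replacement, and the plan permits replacement. The probability under the plan as written cannot be computed, because nothing says how often the sponsor would replace. A reader might also ask for at least 20 evaluable subjects in each arm. The protocol sets no such requirement: its stated target is 40 in total, and the 20 in 17.2 is a judgement of sufficiency that is understandable as per arm from the doubling to 40 and the arms of 23.

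**Conclusion.** The point holds as a minor correction. The stated 46 comes from applying the allowance to the wrong base. At 15% dropout it delivers about 39 fully evaluable subjects before any replacement, and it delivers 40 only if dropout is about 13.0% or less. Applied to those randomized, the same inputs give 47.06, or 48 for equal arms.

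This rests on reading the dropout rate as a proportion of randomized subjects and on counting every dropout as not fully evaluable, which follows from the definition in 9.3. The probability of 0.45 needs two further assumptions, independent dropouts and no replacement, and should not be quoted without them. The finding does not show that the trial is too small or that its results would be biased.

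**What to change.** Reword section 17.2 and the matching synopsis paragraph in one of two ways:

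1. Keep 46 and 40, and say that randomizing 46 allows for a dropout of about 13%.
2. Keep 46 and 15%, and say that about 39 fully evaluable subjects are expected before any replacement under 9.8.3. In that case also align the target of 40 in the synopsis, 8.1 and 9.3.

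Either is a change of wording only, with no extra enrolment and no change to design or analysis. The cost is a slightly less favourable stated figure: a smaller dropout allowance under the first option, or one fewer expected evaluable subject under the second.
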